10.5 Dissemination

We will generate an interactive interface with data customized for each HD, to be used by decision makers to guide scale-up of the multilevel PrEP intervention. Such an interface augments conventional population health modeling data, allowing stakeholders to make informed decisions specific to their population and setting. By integrating cost-effectiveness and budget impact results from each intervention component (PrEP navigator, telehealth PrEP, and digital health platform) into a single interactive tool, decision makers will be able to access a side-by-side comparison of cost and impact estimates specific to their context. Examples of modifiable parameters include: population size, HIV incidence, budget and intervention effectiveness. Decision support tool outputs will include estimated: cost of each component of study intervention implementation (PrEP navigator, telehealth PrEP, digital health platform), cost per person starting PrEP and impact of implementation on number of people starting PrEP. We will work with local partners to make the customizable platform widely available.

11.0 MILESTONES

Milestones are summarized and defined in Table 6. Specific Go/No-Go criteria for proceeding to the R33 phase include the study meets or exceeds the two effectiveness outcome milestones (milestones #5 and 6 in Table 6), and at least four of the six R61 milestones, overall. Due to changes in the study design since initial Notice of Award, including expanding the number of involved sites and revising study design from a cluster randomized trial at the clinic level to a participant-randomized trial, some milestones have been adjusted or adapted to accommodate these differences. Revisions have been incorporated where the original wording is no longer applicable or aligned with the current design. Functionally, these still represent criteria that capture critical administrative, implementation, and effectiveness outcomes which inform decisions regarding proceeding to the next proposed phase of study (R33).

As noted in section 9.0, the study is designed to have adequate statistical power to detect an improvement in PrEP initiation at 3 months of 7.5 percentage points between the intervention arm and control arm. A statistically significant improvement would meet milestone 5. Any other scenarios would be at the discretion of NIH. For milestone 6 (see Table 6), the milestone will be met if at least 50% of those who initiate PrEP sustain

PrEP use for ≥3 months as manifest by follow-up PrEP prescription or ongoing engagement in PrEP care. Any other scenario would be at the discretion of NIH.

For milestone 5, if a statistically significant improvement is not achieved, we will explore whether the intervention is still worth pursuing at the R33 phase with further refinement and development by examining whether there are subgroups (of clients and/or clinics) for which the intervention may be effective. We propose examining the following as part of this assessment, and exploring whether there are revisions that would be worthwhile and feasible to pursue:

Race/ethnicity: U.S. HIV epidemiologic monitoring data documents continued inequities reflected in HIV risk and infection by race/ethnicity with Black/African American and Latinx individuals at higher risk as compared to White individuals. If we find that this intervention is effective for people of color, it would be worth pursuing both from an equity perspective and a cost-effectiveness perspective. For example, a recent modeling study found that PrEP use among Black MSM was substantially more cost-effective as compared to among white MSM (\$33,064 vs \$427,788 per QALY saved)^{56,68}. In contrast, if we find differences by race/ethnicity indicating a stronger effect for white individuals, this may suggest that the intervention succeeded in overcoming some – but not all – structural-level PrEP barriers. In this case, we would explore in the R61 phase whether the barriers seem feasible to address, and if so, focus R33 refinements and intervention mapping more in these areas.

Age: U.S. HIV epidemiologic monitoring data from 2019 showed a decrease in new infections among those in the youngest and oldest age ranges, with no change for those in middle age categories. The document rates are highest among those aged 25-34 (30.1 per 100,000 people) and those aged 35-44 (16.5 per 100,000 people). Literature has also documented greater structural barriers to PrEP access among younger individuals. The components of our intervention aim to address some of these structural barriers (e.g. limited transportation, navigating health insurance, societal stigma)⁶⁸.

Intervention use: Our prior studies using technology-based interventions among MSM and transwomen (including a national sample inclusive of both and North Carolina statewide sample of MSM), have shown that those who use the digital health intervention platform experience a greater intervention benefit than those who do not (i.e. “non-compliant” participants)^{27,69}. Furthermore, while results from our study using HMP among South African adolescent girls and young women are not yet published, preliminary data reflects similarly promising findings⁷⁰. Based on results from the North Carolina study, the U.S. Centers for Disease Control and Prevention (CDC) has identified HMP as a good evidence-based intervention (EBI) for HIV risk reduction⁷¹.

Clinic characteristics: Contextual analyses will be conducted using quantitative and qualitative measures, including intervention engagement (i.e., training attendance, participant enrollment, etc) and interview data from stakeholder interviews to identify possible characteristics and conditions that may facilitate or hinder intervention success, for example, clinic population, on-site PrEP champions, and PrEP delivery model adopted by the clinic. (See Section 6.6)

Progress on all Milestones will be tracked and reported on each annual progress report.

Table 6: Study Milestones

| Year (Quarter) | Milestone | Definition |
|----------------|-----------|------------|
| R61 | | |
| Administrative | | |

| | | |
|------------------------|---|---|
| Y1 ^a (Q2) | (1) Established data use agreement facilitating access to clinic data to assess patient PrEP eligibility and referral | Signed (by clinic-selected designee) letter of support for clinics to participate in STARR-NC; prior to clinic initiating enrollment. |
| Y1 (Q4) | (2) Finalized standard operating manual to cover training, study management and implementation | Written SOPs for study staff, clinic and PrEP navigator training; study specific procedures; and study implementation. |
| Study Implementation | | |
| Y1 (Q4) | (3) Trial enrollment begins by month 12 ^a . | At least 1 clinic prepared to initiate participant screening |
| Y3 (end of trial) | (4) ≥50% of participants complete 6-month survey and return DBS ^b | Among participants who a) received a DBS kit and b) completed their 6-month study period, ≥50% have completed the 6-month survey; ≥50% have returned ≥1 DBS |
| Effectiveness Outcomes | | |
| Y3 (end of trial) | (5) A statistically significant difference in PrEP uptake comparing intervention to control ^c | The proportion of participants who initiated PrEP ^d , is at least 7.5 percentage points higher in the intervention arm than the control arm. This milestone will be met if a statistically significant increase in PrEP initiation is found at 3 months in the intervention arm compared to the control arm. Any other scenarios would be at the discretion of NIH. |
| Y3 (end of trial) | (6) Among intervention arm PrEP initiators, ≥50% sustain use ≥3 months | Among participants in the intervention arm who have initiated PrEP and for whom 3-months of study follow-up time has elapsed since PrEP initiation, at least 50% will sustain PrEP use for ≥3 months as indicated by engagement in PrEP care (on-time visits/refills/injections) and self-reported PrEP use. Any other scenarios would be at the discretion of NIH. We will also report the number of participants who initiate PrEP after their 3-month study visit and thus have less than 3-months of available PrEP sustainment data at their 6-month follow-up visit. |
| R33 | | |
| | Established relationship with HD stakeholders and letters of support | |
| | Refined strategy approved by key stakeholders for implementation | |

| | | |
|--|--|--|
| | Interactive costing interface platform finalized | |
| | Refined strategy $\geq 75\%$ effective (PrEP uptake) vs R61 intervention | |

^a Year 1 refers to the RCT pre-implementation phase aligning with the grant timeline (Budget Period 1: June 13, 2022 – May 31, 2023).

^b Because participants for whom intended follow-up is limited to 3-month outcomes are scheduled to have only 1 DBS, criteria for these participants is as follows: $\geq 50\%$ have completed the 3-month survey, and $\geq 50\%$ have returned 1 DBS. Any other scenarios would be at the discretion of NIH.

^c The original grant proposal specified this milestone as pertaining to PrEP uptake at a clinic level compared to "pre-intervention baseline". However, this is not applicable because revisions to the study now specify randomization will be at the individual (rather than clinic) level with comparison of intervention versus a concurrent control arm. This change describes the effect of the intervention above background uptake in the control arm during the same time (e.g., to control for secular trend). Power analysis suggests that this milestone will reach statistical significance at a 7.5% difference, as clarified in the definition.

^d Persons who self-report taking any PrEP (oral or injection) during a follow-up survey OR in their app will meet this endpoint if this self-report is verified by at least one of the following: (1) an uploaded photo or image demonstrating a PrEP prescription; OR (2) any indication of the presence of tenofovir diphosphate or cabotegravir in DBS; OR (3) staff-abstracted electronic health record of PrEP prescription issued or physician notation of PrEP initiated.

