9.0 STATISTICAL/ANALYTIC CONSIDERATIONS

9.1 Sample Size and Power Estimate

We expect > 7,400 patients will present for care in the 21-month enrollment period, with 20-35% study eligible. Aim 1 analysis includes eligible, consenting patients who successfully download the HMP app. The study will enroll for 21 months with a target sample size of 336. We expect approximately half of participants will be randomly assigned to the intervention arm and the remaining half to the control arm (see Randomization, Section 3.2).

We calculated statistical power for the effect of intervention upon PrEP uptake by 3-month follow-up using SAS 9.4 (Cary, NC) with a 5% type I error rate and a two-sided Chi-square test. Assuming 2.5% of eligible patients start PrEP within 3 months in the control arm, we calculated statistical power to detect a range of small to large effect sizes from 5% to 15% percentage point increases in PrEP uptake under a range of possible sample sizes and assuming 10% missing data (Table 4). At a total sample size of 336, given our design and assumptions, we will have >88% statistical power to detect medium (10%) and large (15%) effect sizes, and 80% statistical power to detect a moderate (7.5%) effect size.

Effect size rationale: As there is currently limited-to-no infrastructure or existing programming providing PrEP in rural North Carolina STI clinics, no prior studies that we are aware of have measured PrEP uptake in these settings. Overall, U.S. PrEP coverage of those assigned male sex at birth with PrEP indications was reported by CDC as 18.4% in January – March 2021, but only 5.6% among Black/African American⁴⁶, who will constitute a large portion of our sample. Among the CDC-designated End-the-Epidemic jurisdictions, recent PrEP coverage estimates of those with PrEP indications range from a low of 4.5% in San Bernardino to a high of 42.3% in San Francisco; North Carolina's state level PrEP coverage estimate is 13.3%, which belies the wide variability from

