9.2.4 Additional Outcome Analyses

Additional analyses will compare self-reported PrEP use among patients who complete the self-administered screening questions (Section 5.4) but who do not enroll in the study (ineligible or eligible but decline). Specifically, we will examine the proportion of respondents endorsing recent or current PrEP use and trends throughout the enrollment period to evaluate “background” PrEP use in the community of patients seeking STI services at participating clinics. We will estimate the proportion reporting PrEP use in each month as the number of patients reporting current PrEP use divided by the number of patients completing the screening questionnaire. We will compute trends in PrEP use by regressing these estimated monthly proportions on time using logistic regression and interpreting the regression coefficient on time.

We will also explore effective-PrEP use, namely PrEP use that aligns with periods of HIV risk^{50,51} using daily app data of tracked sexual behaviors, incident STIs, and PrEP use for persons in the intervention arm. As the daily tracking feature is only in the intervention arm app, this outcome will be exploratory for use in future work.

Additional exploratory analyses will examine PrEP uptake, persistent use, HIV or STI incidence, and intervention satisfaction/preferences at 12-months. All measures will be self-reported and captured using CASI. Only persons who reach the 12-month follow-up visit within the allowable data collection window will have these assessments completed.

We will examine whether there are subgroups (of clients and/or clinics) for which the intervention may be more or less effective (see Section 11.0).

We will also examine the proportion starting PrEP separately for patients enrolled in each calendar year quarter of the study to explore trends over time.

This assessment describes process indicators to inform intervention implementation, optimization, and scale-up. We will measure acceptability of the implementation strategies to providers and clinic directors, feasibility of the intervention, and intervention satisfaction among patients and providers.

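### After a missed milestone 5, Section 11.0 lets a single-subgroup finding support continuing to R33 with no test that the effect differs between subgroups, and it lists a post-randomization factor as a subgroup

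*Combined protocol and SAP*

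**What the plan says.** Section 11.0 sets the Go rule: both effectiveness milestones (5 and 6) and at least four of the six R61 milestones. Milestone 5 is met by a statistically significant increase in 3-month PrEP uptake. Section 11.0 and Table 6 leave any other outcome to NIH discretion.

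Section 11.0 then says what the team will do if milestone 5 is missed. It will consider whether the intervention, with more refinement, still merits the R33 phase by "examining whether there are subgroups (of clients and/or clinics) for which the intervention may be effective". Four factors follow: race/ethnicity, age, intervention use, and clinic characteristics, the last given by example only. One finding carries a stated consequence: "If we find that this intervention is effective for people of color, it would be worth pursuing". A stronger effect in white participants leads to exploring whether the remaining barriers can be addressed in R33.

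Section 9.2.4 says "We will examine whether there are subgroups (of clients and/or clinics) for which the intervention may be more or less effective" and refers back to Section 11.0. Section 9.2 provides a probability difference with 95% CI between arms for binary outcomes. Neither section names an interaction or heterogeneity test, subgroup levels or cut-points, a multiplicity rule, or a subgroup result that would count against continuing.

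**The concern.** The search is triggered only when the overall test has failed. An apparent benefit in one subgroup is then not evidence that the intervention works there: with several subgroups examined, some will look favourable by chance. The relevant question is whether the effect differs between subgroups, and that needs a direct comparison of the subgroup effects. Section 9.2.4 asks this comparative question but gives no method. Section 11.0 attaches its consequence to an effect found within one group.

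Intervention use has a different problem. It is observed after randomization, and control participants get neither the navigator nor the full app (Sections 3.2.1 and 3.2.2), so the control arm has no matching group. Those who use the components may be those already inclined to start PrEP.

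At stake is the quality of the evidence NIH would weigh when deciding on R33 after a null trial.

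**Working it through.** **Inputs from Section 9.1.** The test: "with a 5% type I error rate and a two-sided Chi-square test". The control rate: "Assuming 2.5% of eligible patients start PrEP within 3 months in the control arm". The target: "The study will enroll for 21 months with a target sample size of 336". With 1:1 allocation and the planned 10% missing, 336 × 0.9 / 2 = 151.2 analysed per arm.

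**The plan's own figure.** Section 9.1 claims "80% statistical power to detect a moderate (7.5%) effect size". The normal approximation is

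power = Φ{[δ√n − 1.96√(2p̄(1−p̄))] / √(p₁(1−p₁) + p₂(1−p₂))}, with p₁ = 0.025, p₂ = 0.10, p̄ = 0.0625.

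- n = 151.2: (0.922 − 0.671) / 0.338 = 0.743, power 77.1%.
- n = 168 (no missing data): 81.3%.
- Exact enumeration of the uncorrected chi-square at 151 per arm: 79.7%.

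The 80% is therefore reproduced closely enough to use the same inputs below.

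**Chance of a favourable subgroup under no effect.** Null trials were simulated with 151 per arm and equal uptake in both arms, 20,000 per cell. Trials with overall |z| ≤ 1.96 were kept. The table gives the share with at least one subgroup showing z > 1.96 in favour of the intervention (pooled z-test). Assumptions: three race/ethnicity groups (50/30/20%), two equal age groups and, for 11 subgroups, three further two-level clinic factors split equally.

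| Uptake, both arms | Race/ethnicity and age (5 subgroups) | Plus three clinic factors (11 subgroups) |
|---|---|---|
| 2.5% (protocol) | 4.2% | 8.9% |
| 5% (assumed) | 7.5% | 14.1% |
| 10% (assumed) | 8.7% | 15.0% |

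Other runs of the 11-subgroup case gave 8.6–9.5%, 13.2–15.0% and 14.4–15.6%. For comparison, the overall two-sided 5% test has a nominal 2.5% error in the favourable direction.

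**Effect of also asking for heterogeneity.** This used a separate set of null simulations, with 7 subgroups (factors of 3, 2 and 2 levels) and 13 subgroups (3, 4, 2, 2 and 2). At 2.5% uptake, also requiring a heterogeneity test significant at 5% for some factor lowers the rate from 5.9% to 2.2% (7) and from 8.9% to 2.6% (13). At assumed rates of 5% to 13.3%, it falls from 9.5–10.8% to 3.7–5.2% (7) and from 14.6–18.4% to 5.4–8.5% (13).

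**What the data can show about a true difference.** Take two equal halves (75.6 per arm each), with 7.5 points of benefit in one and none in the other.

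- SE = √[(3 × 0.025 × 0.975 + 0.10 × 0.90) / 75.6] = √(0.163125 / 75.6) = 0.0465.
- Interaction power = Φ(0.075 / 0.0465 − 1.96) ≈ 37%.
- Half-width of the 95% CI = 1.96 × 0.0465 = 9.1 points.
- Power of the test within the benefiting half (76 per arm): 48%.

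**Intervention use.** Suppose no effect and 10% uptake in both arms. Let half the intervention arm be users with 15% uptake and the other half non-users with 5%, purely from prior inclination (assumed). Comparing users with all controls is then significant in about 21% of trials. With 5% overall uptake, split 8% and 2%, it is about 16%. An arm-by-use interaction cannot repair this, because use of these components is not defined in the control arm.

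**The case against.** The strongest reply is that the formal Go rule is untouched. A subgroup finding meets no milestone, and NIH decides if milestone 5 is missed. That is correct, and it limits the point. A reader might infer that the search inflates the chance of a false Go. The documents do not support that: the percentages above are chances of a subgroup signal, and the chance of a Go cannot be computed from the plan.

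A reader might also infer that Phase 2 could be directed at the wrong population, or that an ineffective intervention would simply be carried on. Section 13.1 keeps the Aim 1 enrollment criteria and recruitment for the R33 phase, at all participating clinics. Sections 12 and 13 refine the intervention first and then compare uptake again with the R61 controls. Neither inference stands.

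The plan does not specify a significance test within subgroups, some of its wording is comparative, and the clinic work is partly qualitative. So the simulated rates describe one plausible reading. At 2.5% uptake only about 302 × 0.025 ≈ 7.6 events are expected in the whole trial, and the z-test is unreliable in small subgroups. Also requiring Fisher's exact p < 0.05 lowers the 11-subgroup rates to 3.0%, 8.0% and 9.4% at 2.5%, 5% and 10%, and the five-subgroup rate at 2.5% to 1.2%.

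Finally, at about 37% power, an absolute bar on continuing without an interaction signal would often discard real heterogeneity. That is a fair argument against such a bar. It does not make benefit in one subgroup sufficient.

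**Conclusion.** The point holds as a matter of evidence standard. Section 11.0 lets a within-subgroup finding after a null overall result support the case put to NIH, with no assessment of whether the effect differs between subgroups, and it counts intervention use as a subgroup. Under no effect, the chance of a nominally significant favourable subgroup is about 4% to 9% at the protocol's 2.5% uptake and about 8% to 15% at assumed uptakes of 5% to 10%. These figures rest on assumed subgroup numbers and shares and on a z-test that the plan does not name; an exact test gives lower values. The primary analysis and the formal Go rule are unaffected.

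**What to change.** In Sections 11.0 and 9.2.4:

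- Fix now a short list of baseline subgroup factors with their levels or cut-points, including which clinic characteristics count.
- For each factor, report the arm-by-subgroup difference in risk differences with a 95% CI beside the subgroup estimates, and report all factors whatever the result.
- Remove intervention use from the effectiveness subgroups and report it descriptively within the intervention arm.
- Replace the statement that an effect in one group makes the intervention worth pursuing. State instead that subgroup results after a null overall test are hypothesis-generating, and that significance in one subgroup alone will not be presented to NIH as evidence of effectiveness.

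The cost is wording in two sections, with no new data, visits or participants. The downside is fewer apparent rescue routes after a null result, and interaction intervals that will be wide (about ±9 points in the two-halves example).

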urban to rural areas⁴⁷. Looking to other settings with some comparable characteristics, the THRIVE national CDC demonstration project (n=9538 PrEP-eligible MSM) found a range across study sites of 10.7% to 95.9% (mean 53.8%) of eligible screened participants linked to PrEP services (defined as attending an initial PrEP appointment), with substantially fewer being prescribed PrEP (37.2%). At sites where PrEP navigation was provided, **48.5% of MSM who used navigation were linked to PrEP as compared to 2.8% being linked among those who did not use navigation** ⁴². In a pilot RCT mHealth app (**without navigation**), overall PrEP uptake among a primarily urban MSM population was 12.8% overall (n=6/58) with no difference between intervention and control arms⁴⁸. Among an urban sample of 2106 PrEP-priority eligible MSM attending sexual health clinics in New York City who were offered PrEP navigation services, 288 (13.6%) linked to a PrEP provider and 235 (11.2%) received a PrEP prescription⁴⁹. Looking at these data together and considering the added barriers posed by our rural setting and PrEP stigma, we anticipate being able to see a moderate effect size and have conservatively selected a preliminary intervention efficacy milestone of an observed difference in PrEP uptake of at least 7.5% (see Table 6). This conservative, but still clinically meaningful, effect size will be used as part of the overall determination of whether the intervention approach should be explored further in Phase 2 (see 11.0 Milestones for further discussion).

Based on historical testing data, we expect <2% of all persons who are undergoing HIV screening on day of enrollment to be seropositive. Persons with unidentified HIV at time of enrollment should be randomly distributed between the intervention and control groups. Given the small proportion we anticipate may be enrolled/randomized prior to seropositive results being available, our study remains powered to detect the differences as described above.

Table 4: Statistical power as a function of the observed difference in effect (PrEP uptake) and sample size*

| TOTAL SAMPLE SIZE – R61 PHASE | | | | | |
|------------------------------------|-------|------------|-------|-------|-------|
| OBSERVED DIFFERENCE IN PREP UPTAKE | n=200 | n=300 | n=400 | n=500 | n=600 |
| 5% | 33% | 47% | 58% | 68% | 76% |
| 7.5% | 59% | 77% | 87% | 93% | 96% |
| 10% | 72% | 88% | 95% | 98% | 99% |
| 15% | 92% | 98% | 99% | >99% | >99% |

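### Go/No-Go milestone 5 is stated both as statistical significance and as a difference of at least 7.5 points, which are not the same test; milestone 6 also carries two evidence rules.

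*Combined protocol and SAP*

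**What the plan says.** **Milestone 5 as significance.** Section 11.0: "A statistically significant improvement would meet milestone 5. Any other scenarios would be at the discretion of NIH". The Table 6 title is "A statistically significant difference in PrEP uptake comparing intervention to control", and the second sentence of the definition reads "This milestone will be met if a statistically significant increase in PrEP initiation is found at 3 months in the intervention arm". The fallback to subgroup exploration in 11.0 has the same trigger: "if a statistically significant improvement is not achieved, we will explore whether the intervention is still worth pursuing". Section 11.0 uses 7.5 points only as the design difference, calling the study "designed to have adequate statistical power to detect an improvement in PrEP initiation at 3 months of 7.5 percentage points".

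**Milestone 5 as a 7.5-point difference.** The first sentence of the Table 6 definition says the proportion initiating PrEP "is at least 7.5 percentage points higher in the intervention arm than the control arm". Section 9.1 says the team selected a "preliminary intervention efficacy milestone of an observed difference in PrEP uptake of at least 7.5" percent, cites Table 6 for it, and says this effect size will form part of the decision on Phase 2. It also refers to 11.0 for more detail. Footnote c to Table 6 joins the two rules, saying that the power analysis indicates significance will be reached at a 7.5% difference and that the definition clarifies this.

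**Milestone 6.** Section 11.0 counts an initiator as sustaining use on the evidence of either a follow-up prescription or continuing engagement in care. Table 6 asks for engagement in care together with self-reported use. It also limits the denominator to intervention-arm initiators with three months elapsed since initiation, a limit that the sentence in 11.0 does not state.

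**Weight.** The Go/No-Go criteria require that the study "meets or exceeds the two effectiveness outcome milestones", plus at least four of the six R61 milestones overall. Other scenarios for milestones 5 and 6 are left to NIH.

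**The concern.** A Go/No-Go rule should give one answer for any given dataset. Nothing in the plan says whether 7.5 points is an extra condition, an alternative to significance, or only the true difference assumed for power. The word 'observed' in 9.1 makes the last reading hard to apply there. Footnote c treats the two tests as one, but a difference that a trial has 80% power to detect lies well above the smallest observed difference that reaches significance. A significant result of, say, 6 points would therefore meet the milestone under 11.0 and fail it under 9.1 and the opening sentence of the definition.

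For milestone 6, an initiator with a refill on record but no self-reported use (for example, after a missed survey) counts under 11.0 and not under Table 6.

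The stake is the decision to move to the R33 phase. With both wordings in place, the criterion can be argued once results are known.

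**Working it through.** **Inputs (9.1 and the Table 4 note).** Total 336, 1:1, so 168 per arm; 10% missing, so 168 × 0.9 = 151.2, taken as 151 per arm; control uptake 2.5%; planned uptake 2.5% + 7.5 points = 10%; two-sided 5% chi-square test. Section 9.2 analyses binary outcomes by a probability difference with a 95% CI; its form is not given, so Wald is assumed where it is used below.

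**The plan's own figure.** Section 9.1 states 80% power for 7.5 points at N = 336. Pooled normal formula: power = Φ{[Δ − 1.96·√(2p̄(1−p̄)/n)] / √[(p₁(1−p₁)+p₂(1−p₂))/n]}, with Δ = 0.075 and p̄ = 0.0625.
- n = 168: (0.075 − 1.96 × 0.02641)/0.02609 = 0.890, power 81.3%.
- n = 151.2: (0.075 − 1.96 × 0.02784)/0.02750 = 0.743, power 77.1%.
- Exact binomial enumeration of the uncorrected chi-square at n = 151: 79.7%.

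The stated 80% is reproduced by the first and third of these.

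**Where significance starts.** For a control starts and b intervention starts at n = 151 per arm, z = [(b−a)/n] / √[p̄(1−p̄)·2/n], with p̄ = (a+b)/(2n). For a = 4, b = 12: difference 8/151 = 5.3 points, p̄ = 16/302 = 0.0530, SE = 0.0258, z = 2.06, p = 0.040. With b = 11, p = 0.064.

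| Control starts | First significant intervention count | Difference | p |
|---|---|---|---|
| 3 | 10 | 4.6 points | 0.047 |
| 4 | 12 | 5.3 points | 0.040 |
| 5 | 14 | 6.0 points | 0.033 |

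With 4 control starts, 15 intervention starts give 11/151 = 7.3 points (p = 0.009), and 7.5 points is first passed at 16 starts (12/151 = 7.9 points, p = 0.006). So 12 to 15 starts satisfy one statement of the milestone and not the other.

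**How often the two rules disagree.** Each probability is the sum, over all (a, b), of Bin(a; n, p₁)·Bin(b; n, p₂) for the outcomes that satisfy the rule. Significant means z > 1.96 in favour of the intervention.

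| True rates, n per arm, test | Significant | At least 7.5 points | Significant, below 7.5 | At least 7.5, not significant |
|---|---|---|---|---|
| 2.5% vs 10%, 151, chi-square | 79.7% | 47.6% | 32.0% | 0.0% |
| 2.5% vs 10%, 151, Wald CI | 80.2% | 47.6% | 32.5% | 0.0% |
| 2.5% vs 10%, 168, either test | 83.9% | 50.3% | 33.6% | 0.0% |
| 2.5% vs 12.5%, 151, chi-square | 93.6% | 78.7% | 14.9% | 0.0% |
| 2.5% vs 17.5%, 151, chi-square | 99.7% | 98.8% | 0.9% | 0.0% |
| 5% vs 12.5%, 151, chi-square | 64.6% | 48.2% | 16.4% | 0.0% |
| 10% vs 17.5%, 151, chi-square | 47.5% | 48.7% | 1.4% | 2.6% |

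In the first row, 32.0/79.7 = 40% of significant trials fall below 7.5 points. The 47.6% is expected: if the true difference is 7.5 points, the observed one reaches it about half the time. The 5% and 10% control rates are illustrative assumptions; the plan uses only 2.5%.

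**Milestone 6.** No arithmetic applies. One text joins its two kinds of evidence with 'or', the other with 'and', and only 11.0 lets a prescription or engagement suffice without self-report. The documents give no figure for how many initiators this would affect.

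**The case against.** The best reply is that significance is plainly the operative rule. Only the significance sentences say when milestone 5 is met, the fallback is triggered by non-significance, 11.0 places 7.5 points in its power statement, and 9.1 calls its version preliminary and defers to 11.0. This is the likeliest reading and the natural way to resolve the conflict. It does not remove the threshold from the definition itself, and 9.1 cites Table 6 as well as 11.0.

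NIH discretion means that missing a milestone is not an automatic No-Go, and rewording would not end that discretion. But it covers other scenarios, and whether a significant 6-point difference is one of them is what the text leaves open.

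Footnote c can be read more kindly: at the planned control rate, an observed 7.5 points is indeed significant. It still does not follow that significance implies 7.5 points, as the link to the definition suggests.

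The one-in-three figure belongs to the planned effect. It shrinks with a larger effect or a higher control rate, and at 10% control uptake a small reverse conflict appears. That stands, and the range is shown above.

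For milestone 6, 11.0 names Table 6 as the place where milestones are defined. That favours the Table 6 wording, but 11.0 also states in its own words when the milestone is met, and the two differ.

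**Conclusion.** The concern holds. Milestone 5 has two non-equivalent statements in the current text. With 151 analysed per arm and the planned 2.5% versus 10%, they give different answers in 32.0% of trials (32.5% with a Wald interval, 33.6% with no missing data), always in the direction of significant but below 7.5 points. The chance of meeting the milestone is 79.7% on one reading and 47.6% on the other. The disagreement falls to 16.4% at 5% versus 12.5%, and to 14.9% if the true effect is 10 points over a 2.5% control rate. Milestone 6 has two evidence rules and two denominators; the size of that effect cannot be derived from the documents.

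This is a contradictory decision threshold and should be fixed. It does not touch the primary estimate, its analysis or the sample size.

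**What to change.** Before results by arm are seen, and with the funder's agreement:

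- State one milestone 5 rule in the same words in 9.1, 11.0 and Table 6. If it is significance, which the text already makes sufficient, describe 7.5 points as the true difference assumed for power, and replace the observed-difference wording in 9.1 and the first sentence of the Table 6 definition.
- If an observed 7.5 points is meant to bind, say so, and report that the chance of reaching it at the planned effect is about 48%. This is compatible with 80% power to detect that effect.
- Reword footnote c so that it no longer equates significance with a 7.5-point difference.
- Give milestone 6 one evidence rule and one denominator in 11.0 and Table 6, stating whether self-reported use is required.

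The cost is wording in those places plus the funder's agreement. Data collection, sample size and the primary analysis do not change.
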